Participants taking Internet surveys will provide informed consent and complete the REDCap-enabled surveys in the language of their choice, English or Spanish. Participants will be surveyed at approximately 1-2 and 13-24 months after enrollment, and at the end of surveillance.

To complement the patient perspective, we will also design a brief survey to capture provider satisfaction with the assigned protocol for surveillance and their perception about barriers to its implementation. Development of the brief physician survey will be led by [name] at UCSF, based on her ongoing qualitative pilot study of physician attitudes and beliefs about cancer screening.^{57,58} The survey will primarily focus on radiologists and ordering providers (pulmonologists and thoracic surgeons) at each study site, because they are most directly involved with lung nodule evaluation, although we will explore the possibility of surveying primary care providers. Surveys will be distributed to radiologists and ordering providers at the start of the trial and near the end of the study enrollment period (approximately mid-way through the trial).

Aim 3 Outcomes, Nodule-Related Resource Utilization and Radiation Exposure: We will compare health care resource utilization between groups by conducting searches of structured data in EHRs for relevant ICD-9 procedure codes that appear during the surveillance period (from date of the index CT scan to the date of first cancer treatment or 2 years of follow-up, whichever comes first). Most study sites use the Epic EHR, which allows for efficient searching of utilization tables; other EHR systems have similar capabilities. We will capture all relevant imaging tests (chest CT, PET,), invasive biopsy procedures (bronchoscopy, transthoracic

needle biopsy), thoracic surgical procedures, outpatient visits, emergency department visits and hospitalizations, as we have done previously for the NCI and VA-funded CanCORS study.⁵⁹ We will also record procedure-related complications by searching for diagnostic codes for pneumothorax, respiratory failure and major bleeding (relying in part on operational definitions created by the Agency for Healthcare Research & Quality Patient Safety Indicators).⁶⁰

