The primary study objectives include, among individuals with small pulmonary nodules identified either incidentally or by screening, comparing more vs. less intensive CT surveillance for the progression of cancer beyond AJCC 7th edition stage T1a disease (or T1b in the AJCC 8th edition) (Aim 1), nodule-related emotional distress (Aim 2), health care resource utilization and exposure to diagnostic radiation (Aim 3), and overall adherence with the recommended surveillance protocol (Aim 4).

The secondary objectives include comparing more vs. less intensive CT surveillance for the timeliness of lung cancer diagnosis and overall survival of patients in each study arm who prove to have a cancerous nodule (Aim 1), patient general health status and satisfaction with the evaluation process and the provider satisfaction with the surveillance protocol and the evaluation process (Aim 2), and adherence to use of low radiation-dose techniques (Aim 4). In general, we hypothesize that more intensive follow-up will result in more CT imaging (by design), greater radiation exposure, more downstream testing, greater anxiety and emotional distress, slightly shorter times to cancer diagnosis, and worse adherence to follow-up, and no effect on cancer stage distribution or overall survival.

Primary endpoints:

Aim 1: Proportion of lung cancers that are greater than 20mm

- Measured as progression beyond AJCC 7th edition T stage of T1a or, equivalently, AJCC 8th edition T stage of T1b

Aim 2: Nodule-related anxiety and emotional distress at 1-2 months, 13-24 months, and ≥25 months after nodule identification

- Measured using the IES-R and STAI-6

Aim 3:

1. Health care resource utilization within 26 months following nodule identification
 - Number of visits within 26 months of nodule identification, including the following exams (separate analyses by type of exam):
 - Chest CT scans
 - Chest x-rays
 - PET or PET/CT scans
 - Biopsies (look separately and together): Bronchoscopic biopsy, percutaneous biopsy, surgical biopsy/resection, extrapulmonary biopsy.
 - We will not include any exams after the date of cancer diagnosis, but will include biopsy that led to the cancer diagnosis
2. Serious complications within 7 days and within 30 days of a chest CT, chest x-ray, PET or PET/CT scan, or biopsy (bronchoscopic biopsy, percutaneous biopsy, surgical biopsy/resection, extrapulmonary biopsy) performed within 26 months of baseline CT:
 - Pneumothorax

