Descriptive statistics will be generated for radiation exposure and frequency of follow-up CT scans and other nodule-related resource utilization will be obtained by site and study arm. For each type of nodule-related resource utilization, we will also create a binary variable to indicate whether a patient has any exam of that type (1 yes and 0 no) and obtain the corresponding frequency. For H3a, to examine whether among all participants with a lung nodule ≤ 15 mm, more intensive surveillance will be associated with a greater number of specific follow-up tests and types of follow-up tests (e.g., imaging, non-surgical biopsy, surgery), we will use mixed-effects Poisson regression model including random site effects to account for clustering of patients within sites. We will also model the frequency at which at least 1 specific follow-up test or type of follow-up test is performed using hierarchical logistic regression that includes random site effects. All regression models mentioned above will be fitted with and without potential confounders including age, gender, ethnicity/race, smoking, BMI, nodule size, and any facility-level factors balanced during the randomization. For H3b, to examine whether among all participants with a lung nodule ≤ 15 mm, more intensive surveillance will be associated with a greater number of serious complications related to invasive procedures, similar strategy used for H3a will be adopted. We will model the number of serious procedure-related complications using mixed-effects Poisson regression models and the frequency of patients with any serious complications using hierarchical logistic regression models. For H3c, to investigate whether all participants with a lung nodule ≤ 15 mm, more intensive surveillance will be associated with greater total exposure to diagnostic radiation than less intensive surveillance, we will use mixed effects models and log-transform the radiation exposure to make normal assumption more appropriate.

For H4, binary variables will be generated to indicate adherence to the recommended protocols measured at the level of the ordering provider and the patient. Cross tabulations of the

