We will continue recruitment through the end of the study to collect additional data for HTE analyses with greater statistical power for Aim 1. We assume 10% loss to follow-up before final diagnosis is established based on KPSC membership data. This yields an estimated sample size for analyses of 960 individuals with cancerous nodules for Aim 1, and 32,000 individuals with small nodules for Aims 2-4.

Aim 1: For the primary outcome, the baseline risk of progression has not been reported. Conservatively, we assume that 5% of patients will progress from a tumor ≤ 15 mm to a tumor > 20 mm during the surveillance period. Assuming a two-sided alpha of 0.05, and an intraclass correlation coefficient (ICC) of 0.01, a sample size of 888 unique patients with cancerous lung nodules (444 per arm) is required to achieve 83% power to detect an absolute increase in tumor progression of 5 percentage points. Thus, our anticipated sample size of 960 unique patients with cancerous lung nodules provides adequate power to show non-inferiority of the less intensive surveillance strategy for our primary outcome of lung cancer stage $> T1a$ at diagnosis. The most uncertainty in our assumptions is for the ICC. We will have at least 80% power to detect a 5% increase in our primary outcome for ICC values of 0.012 or less. At the baseline ICC value of 0.01, a total sample size of 32,560 enrolled (including 888 patients with cancerous nodules) will have 0.83 power; for an ICC value of 0.012, a total sample size of 35,200 enrolled (960 patients with cancer) will also have 0.83 power.

Aim 2: Prior studies of anxiety and distress in lung cancer screening have shown that the identification of a lung nodule leads to anxiety and emotional distress that subsequently dissipates over 1-2 years.^{56 63 52} For our analyses of anxiety and emotional distress, we will have $> 90\%$ power to detect an effect size of 0.22 standard deviation, assuming an ICC of 0.01, even if the response rate is as low as 5%, resulting in an estimated sample size of approximately 792 respondents in each arm.

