Despite these efforts, we expect to have some data missing at random because of information not being documented in the EHR, as opposed to informatively missing, where the probability of being missing depends on the missing value. Thus, we will use multiple imputation methods to account for missing data.^{64,65} In addition, we will report and compare the characteristics of patients with and without missing data. We expect a maximum of 10% of patients to be lost to follow-up within 2 years of the index CT scan. To minimize missingness of cancer outcomes on these patients, we will link with cancer registries from states with a participating site. Sites will document the date when patients disenroll or die and the last patient encounter in the health system. We will censor these patients in time-to-event analyses. For analyses restricted to patients with a lung cancer diagnosis, we will perform sensitivity analysis to determine the potential effects of incomplete capture of lung cancers in patients who disenroll. For example, we will assume some percentage of these patients were diagnosed with lung cancer and vary the percentage with stage >T1a tumors.

Patient and Stakeholder Engagement

This collaboration between scientists, patients and multiple stakeholders will be guided by the PCORI engagement principles: reciprocity, co-learning, partnership, trust, transparency and honesty. The PIs have identified key stakeholders who have agreed to serve as study partners and assist us with study design and execution and interpretation and dissemination of results. The preliminary governing structure that we developed is illustrated in the Figure.

This structure will facilitate interactions between each of the following groups:

Executive Committee (EC): The EC will include the 4 study PIs, 1 patient stakeholder, 1 non-patient stakeholder, and 1 site PI. The EC will provide an efficient forum for discussion of all study-related issues and a mechanism for rapid decision-making when necessary. The EC will meet during monthly conference calls.

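### Aim 3 exam counts are modelled without time observed, so patients lost before the window closes would by default enter as complete 26-month counts

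*Combined protocol and SAP*

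**What the plan says.** - **Endpoint.** Primary endpoints, Aim 3, item 1 is "Number of visits within 26 months of nodule identification", analysed separately by exam type. The only truncation given is at cancer diagnosis: "We will not include any exams after the date of cancer diagnosis, but will include biopsy that led to the cancer diagnosis".
- **A second window.** The Aim 3 paragraph under Outcomes runs utilization "from date of the index CT scan to the date of first cancer treatment or 2 years of follow-up, whichever comes first". Both the length and the stopping event differ from the endpoint list.
- **Model.** The Aim 3 analysis section says "we will use mixed-effects Poisson regression model including random site effects to account for clustering of patients within sites". A hierarchical logistic model is added for having at least one exam of a type. H3b (serious complications) follows the same strategy. No offset, person-time or completeness rule appears.
- **Loss.** The Missing Data section says "We expect a maximum of 10% of patients to be lost to follow-up within 2 years of the index CT scan". For patients who leave it gives registry linkage for cancer outcomes, a sensitivity analysis for analyses restricted to lung cancer patients, and one further rule: "We will censor these patients in time-to-event analyses". It also has sites record the dates of disenrolment, death and last encounter.
- **Who is analysed.** The intention-to-treat population is every patient with a qualifying nodule. The power section, after allowing for 10% loss, works with "32,000 individuals with small nodules for Aims 2-4".
- **Length of follow-up.** The sample size section promises at least 2 years per patient, not 26 months.

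**The concern.** An exam count taken from health records carries no missing-data flag. If a patient disenrols at month 8, any later scan elsewhere is simply absent, and the patient's count looks like any other low count. With all enrolled patients analysed and no exposure term in the model, that partial count is treated as 26 months of experience. The any-exam indicator has the same difficulty: a 0 may mean no exam or no observation. Some patients who are not lost may also lack the last two months, because follow-up is assured only to 2 years.

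The estimated mean counts then depend on how long patients were observed as well as on the assigned protocol. If observation time differs between arms, so does the bias, and it reaches the rate ratio.

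The plan recognises unequal capture elsewhere. For Aim 1 it adds a modified intention-to-treat analysis whose definition differs between integrated and other systems. Aim 3 has no counterpart.

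**Working it through.** **1. The plan's own figure.** Inputs from the Aim 3 power paragraph and the sample size section: 32,000 patients, 24 clusters, ICC 0.01, two-sided alpha 0.05, difference 0.14 SD.

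- Mean cluster size: 32,000/24 = 1,333.3
- Design effect: 1 + 1,332.3 × 0.01 = 14.32
- Effective n per arm: 16,000/14.32 = 1,117
- Power for 0.14 SD: 0.911. The difference detectable at 90% power is 0.137 SD.

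The stated 90% for 0.14 SD is reproduced. The point is an omitted rule, not an arithmetic error. (35,200/1.1 = 32,000; 35,200 × 0.9 = 31,680.)

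**2. Effect of ignoring observed time.** Let d be the share lost and u the mean unobserved fraction of the window among those lost. With a constant exam rate and a true mean μ, the recorded mean is μ(1 − d·u). Assumptions:

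- u = 0.5 (loss spread evenly), range 0.25 to 0.75.
- μ = 3.5 in the more intensive arm (the plan's assumed procedures per patient).
- μ = 3.5 × 0.7 = 2.45 in the less intensive arm. This applies the planned reduction in imaging of about 30% to that count, for illustration only.

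The true ratio is 3.5/2.45 = 1.429 and the true difference is 1.050.

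| Loss, more / less intensive | Recorded means (u = 0.5) | Ratio (range over u) | Difference |
|---|---|---|---|
| 10% / 10% | 3.325 / 2.328 | 1.429 (unchanged) | 0.998 |
| 5% / 10% | 3.413 / 2.328 | 1.466 (1.447–1.487) | 1.085 |
| 10% / 5% | 3.325 / 2.389 | 1.392 (1.373–1.411) | 0.936 |

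- Equal loss: means and difference fall by 0.10 × 0.5 = 5% (2.5% at u = 0.25, 7.5% at u = 0.75).
- Five-point imbalance: (1 − 0.05 × 0.5)/(1 − 0.10 × 0.5) = 0.975/0.95 = 1.026, a shift of 2.6% (1.3% at u = 0.25, 4.1% at u = 0.75). With the imbalance reversed, the ratio falls by 2.6% (1.3 to 3.9%).

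The 10% refers to 24 months. At an assumed constant hazard, loss by 26 months is 1 − 0.9^(26/24) = 10.8%.

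**3. Does an offset repair it?** Poisson counts were simulated with two million patients per arm and exit uniform over the window. The ratios without an offset were 1.426, 1.467 and 1.392 for the three rows. With observed time as exposure they were 1.427, 1.430 and 1.429. Exit was non-informative by construction.

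**4. Does equal loss distort the ratio through scan timing?** Expected scans are the sum over scheduled months t of (1 − 0.10 × t/26). Group A at months 3, 9, 24 gives 3 − 0.10 × 36/26 = 2.862. Against three Group B rows:

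- 12, 24 (solid, about 6 to 8 mm): 2.862/1.862 = 1.537 against 1.500, +2.5%.
- 3, 15 (solid >8 mm; month 27 falls outside the window): 2.862/1.931 = 1.482 against 1.500, −1.2%.
- 6, 18 (multiple solid, 6 to 8 mm): 2.862/1.908 = 1.500, no change.

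There is no general direction.

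**5. Could the conclusion change?** The standard error from step 1 is √(2/1,117) = 0.042 SD. The documents give no SD for the count. Assuming 1.9 to 2.5 with a mean of 3.5, this is 2.3 to 3.0% on the ratio. The planned contrast, ln(1.429) = 0.357, lies 0.357/0.030 = 11.9 to 0.357/0.023 = 15.5 standard errors from no difference.

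**The case against.** **The documents do not say that unobserved time is scored as no utilization.** This is correct. The Missing Data section lists leaving the health system as one of its two types of missing data and then prescribes multiple imputation. The 32,000 in the power section suggests that lost patients are dropped. Neither settles the matter: imputation is introduced for information not documented in the health record, nothing marks a leaver's count as missing, and dropping leavers conflicts with the stated intention-to-treat population. Full-window scoring is the likely default, not a stated rule.

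**Unequal loss between arms is assumed.** This stands too. Outside KPSC, Table 1 shows 6 of 7 more-intensive clusters in non-integrated systems against 3 of 6 less-intensive ones, which invites the inference that loss is unequal. But KPSC supplies 11 of the 24 clusters and is in both arms. About 22,000 of the 35,200 patients are expected at California sites. Setting type and KPSC status were balanced at randomization, and the adjusted models include the balanced facility factors. Loss by arm is unknown.

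**The main contrast is built into the design.** A reader might infer an inflated false-positive rate for Aim 3. The documents do not support that. A null for total imaging is excluded by design (step 5). For invasive testing, where a null is more plausible, the plan's 3.4 points detectable at 90% power implies a standard error near 3.4/3.24 = 1.05 points, or 21% of the 5% baseline. A 2.6% shift is then about 0.12 standard errors.

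**Equal loss need not bias the ratio.** A reader might infer that it always does, because Group A scans come early. Step 4 shows that this depends on the nodule row and can go either way.

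**Death and cancer diagnosis are not missing data.** Agreed. A patient who has died has no further exams, and stopping at diagnosis is part of the endpoint. Ending exposure at either would change the quantity being estimated.

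**Conclusion.** The point holds as an analysis gap that should be closed. The Aim 3 count and any-exam models have no term for time observed and no stated rule for patients who leave before the window ends, and H3b inherits this.

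If partial counts enter as complete ones, 10% loss in both arms understates the mean counts and the absolute difference by about 5% (2.5 to 7.5%). An assumed 5-point imbalance in loss moves the rate ratio by about 2.6% (1.3 to 4.1%). These figures rest on a constant exam rate, exit unrelated to utilization, and a mean unobserved fraction of 0.25 to 0.75. The imbalance is an illustration, because the documents give no loss by arm or site.

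The size of the estimated utilization effect, a primary Aim 3 endpoint, is at risk. The direction of the CT contrast is not.

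**What to change.** In the Aim 3 analysis section:

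1. State one observation window, reconciling the 26 months and the stop at diagnosis in the endpoint list with the 2 years and the stop at first treatment under Outcomes.
2. End each patient's observation at the earlier of window end and disenrolment. Treat exams after cancer diagnosis as excluded by definition, and death as a terminal event with no further exams. Neither is missing time.
3. Model counts in intervals with log observed time as offset, arm-by-interval terms and the planned random site effects. Report the mean count per arm at the end of the window. The interval terms matter because scheduled scans are not evenly spaced.
4. Analyse any exam as cumulative incidence with disenrolment censored and death as a competing event, or in fully observed patients, keeping the allowance for clustering.
5. Apply the same exposure rule to H3b.
6. For sites without disenrolment dates, state the rule used. Add sensitivity analyses using last encounter as the end of observation and using fully observed patients only. The offset does not correct for informative exit, so also report observed time by arm.

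The cost is SAP wording and programming, using dates that sites are already asked to record, and slightly wider intervals.
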